## 12.3 Discontinuation of Treatment and Withdrawal of Patients

The reasons a patient may discontinue or be withdrawn from the study include, but are not limited to, adverse events, disease progression, patient request, Investigator decision, protocol violation, patient noncompliance, and study termination by the Sponsor.

When a patient discontinues or is withdrawn, the Investigator or designee will notify the Sponsor (or designee) and should perform all End of Treatment and follow up procedures as indicated in the Schedule of Study Assessments ([Attachment 1](#)) after discontinuation of study treatment. The Investigator or designee must document in the source if the patient withdrew consent from treatment/ study procedure only or from treatment/ study procedures and from further contact.

### 13.0 STUDY DRUG AND OTHER STUDY TREATMENTS

Study treatment is defined as any investigational treatment(s) or marketed product(s) intended to be administered to a study subject according to the study Protocol. There are 2 investigational study treatments in this study – INCB001158 and pembrolizumab. INCB001158 is also referred to as the study drug in this Protocol. Although pembrolizumab is approved and marketed in various indications, it is investigational in this study in combination with INCB001158.

#### 13.1 Study Treatment Administration

##### INCB001158

Study drug (INCB001158) needs to be taken orally as capsule or tablet (25 mg or 100 mg per capsule or tablet) formulation. INCB001158 will be administered only to patients who have signed and dated an Informed Consent Form. Patients in Part 1a and 2: INCB001158 needs to be taken on Days 1 through 28 of each 28-day cycle and should be taken orally using the number of capsules or tablets directed in the Pharmacy Manual. [REDACTED]

[REDACTED] Patients in Part 1b and 3: INCB001158 needs to be taken on Days 1 through 21 of each 21-day cycle and should be taken orally using the number of capsules or tablets directed in the Pharmacy Manual. INCB001158 dosing will not be adjusted for body weight or surface area. Patients will continue to receive INCB001158 until disease progression (per irRECIST), intolerable toxicity, patient withdraws consent, or the Investigator determines that it is not in the patient's best interest to remain on study.

The study drug should be taken by the patient at approximately the same times each day on an empty stomach with a full glass of water. The first dose should be taken at least 2 hr before breakfast. The evening dose of INCB001158 will be taken approximately 12 hr later and at least 2 hr before or 1 hr after eating a meal. The effect of food is being evaluated in Part 1a during monotherapy dose escalation. If it is demonstrated that improved bioavailability can be achieved by taking INCB001158 with food, then patients thenceforth will take the drug with breakfast and dinner.

On PK days (see [Attachment 1](#)) patients should be instructed NOT to take their morning dose of INCB001158 at home. The morning dose must be administered at the clinical site after all pre-dose procedures have been performed. The time of dosing will be recorded in the clinic.

The evening doses will be self-administered by the patient after all post-dose activities have been complete.

Patients enrolled in the pembrolizumab combination cohorts (Part 1b and Part 3) will have all pre-dose procedures performed prior to receiving pembrolizumab. Once the pembrolizumab infusion is complete, patients should be instructed to take their morning dose of INCB001158. Breakfast should not be eaten until at least 2 hr after taking INCB001158. The time of dosing will be recorded in the clinic. The evening dose of INCB001158 will be taken by the patient as usual. On non-PK collection days, patients will take INCB001158 per their usual administration schedule.

Patients who vomit their INCB001158 dose should be instructed NOT to make up that dose and to report the frequency of vomiting occurrences associated with study drug administration to the site. Patients who report  $\geq 3$  incidences of vomiting associated with study drug administration will have a blood sample drawn for an unscheduled PK analysis.

#### Pembrolizumab

Pembrolizumab will be administered on day 1 of each 3-week treatment cycle after all procedures and assessments have been completed as detailed on the schedule of assessment. Pembrolizumab will be administered as a dose of 200 mg using a 30-minute IV infusion. Sites should make every effort to target infusion timing to be as close to 30 minutes as possible. However, given the variability of infusion pumps from site to site, a window between -5 minutes and +10 minutes is permitted (i.e., infusion time is 30 minutes -5 min/+10 min). Patients will continue to receive pembrolizumab until disease progression (per irRECIST), intolerable toxicity, patient withdraws consent, or the Investigator determines that is not in the patient's best interest to remain on study. The maximum duration of pembrolizumab treatment on study will be up to 35 doses (approximately 2 years).

Pembrolizumab (Keytruda®) is supplied either as a 50 mg, lyophilized powder in single-use vials for reconstitution or as a 25 mg/mL sterile solution for infusion in 4 mL vials. The dose recently approved in the United States and several other countries for treatment of melanoma patients is 2 mg/kg Q3W. Please refer to the pembrolizumab Label/Investigator's Brochure for specific instructions on pembrolizumab administration.

### 13.2 Packaging and Labeling

INCB001158 capsules and tablets (25 and 100 mg) are manufactured, packaged, and labeled according to current Good Manufacturing Practices (cGMP). All product labels will be in the local language and will comply with the legal requirements of each country. For additional information, please refer to the Pharmacy Manual.

Pembrolizumab is available either as 50 mg, lyophilized powder in single-use vials or as a 25 mg/mL sterile solution for infusion in 4 mL vials (3). The product label will be in the local language and will comply with the legal requirements of each country. For additional information, please refer to the pharmacy manual.

### 13.3 Storage and Stability

#### INCB001158

INCB001158 capsules and tablets will be stored at the clinical site, as indicated on the study drug label, i.e., room temperature, between 15°C - 30°C (59°F - 86°F).

Patients will be requested to store the study drug at the recommended storage conditions noted on the label, out of the reach of children.

#### Pembrolizumab

Pembrolizumab vials should be stored under refrigeration at 2°C - 8°C (36°F - 46°F). Protect from light by storing in the original package until time of use. Do not freeze or shake. For procedures for the proper handling, storage, preparation and administration of pembrolizumab, please refer to the Pembrolizumab Label/Investigator's Brochure.

### 13.4 INCB001158 Accountability, Reconciliation, and Return

On Day 1 of Cycle 1, patients will be provided with enough INCB001158 to last until their next clinic visit. For patients in Parts 1a and 2, patients will return on Day 1 of each cycle thereafter and will receive a 28-day supply of INCB001158; the number of capsules or tablets remaining from the previous visit will be counted and recorded.

For patients in Parts 1b and 3, patients will return on Day 1 of each cycle thereafter and will receive a 21-day supply of INCB001158; the number of capsules or tablets remaining from the previous visit will be counted and recorded.

The Investigator or designee must maintain an accurate record of dispensing the study drug in a Drug Accountability Log, a copy of which must be given to the Sponsor at the end of the study. The Drug Accountability Log will record the study drugs received, dosages prepared, time prepared, doses dispensed, and doses destroyed. The Drug Accountability Log will be reviewed by the field monitor during site visits and at the completion of the study.

If evidence of tampering is observed, notify the Sponsor and return the questionable INCB001158 shipment with the appropriate form to the contract distribution center. Returned and unused INCB001158 study drug may also be destroyed and documented at the investigative site in accordance with approved site/institution standard operating procedures.

### **13.5 Study Treatment Compliance**

Compliance with all study-related treatments should be emphasized to the patient by the site personnel, and appropriate steps should be taken to optimize compliance during the study. Compliance with INCB001158 will be calculated by the sponsor based on the drug accountability documented by the site staff and will be monitored by the sponsor/designee (capsule/tablet counts). Patients will be instructed to bring all unused INCB001158 capsules/tablets with them to the study visits from Cycle 2 Day 1 onwards, in order for site personnel to conduct capsule/tablet counts to assess study treatment accountability. The drug accountability documentation will be used by the sponsor to calculate treatment compliance. Missed doses of INCB001158 should be skipped. If a patient forgets to take a dose of study drug and he/she is outside of the allotted window period ( $\pm 6$  hr), he/she should be instructed NOT to take extra study drug at their next administration.

## 14.0 MEASURES TO MINIMIZE/AVOID BIAS

Each patient will be assigned a unique number and will keep this number for the duration of the study. Patient numbers will not be reassigned or reused for any reason. Patients should be identified to the Sponsor only by their assigned number, initials (not required for EU), date of birth, and sex. The Investigator must maintain a patient master log.

## 15.0 STATISTICAL ANALYSIS

### 15.1 General Statistical Considerations

Protocol INCB 01158-101 is a Phase 1 multicenter, open-label study in patients with advanced and metastatic solid tumors.

Since this is an open-label clinical trial, descriptive statistics will be employed to analyze the data by tumor type and dose level. Summary statistics for continuous variables will include the mean, standard deviation, median, and range (minimum/maximum). Categorical variables will be presented by tumor type as frequency counts and percentages, and time-to-event variables will be summarized by Kaplan-Meier plots, medians, and ranges.

The data will be tabulated and analyzed with respect to patient enrollment and disposition, demographic and baseline characteristics, prior and concomitant medications, efficacy, and safety measures. The efficacy analysis will be conducted on the Efficacy Evaluable Population, and the safety analysis will be performed on the Safety Population (see Section 15.3.1).

All confidence intervals will be constructed at the 95% confidence level. Data listings will be created to support each table and to present all data collected.

### 15.2 Sample Size and Power

**Dose Escalation:** The goal is to determine a dose level of INCB001158 for which the rate of DLTs is less than 33%. Up to approximately 108 patients are planned for single agent dose escalation (Part 1a) and 108 patients for combination dose escalation (Part 1b), both including backfill patients.

**Dose Expansion:** For Expansion Cohorts in Parts 2 and 3 (except the initial part of Cohort 2c), Simon's two-stage design (Simon 1989) will be used as outlined in Table 15.2-1 below. The null hypothesis that the true response rate is  $[p_0]$  will be tested against a one-sided alternative. In the first stage,  $[n_1]$  patients will be accrued. If there are  $[r_1]$  or fewer responses in these  $[n_1]$

patients, the study will be stopped. Otherwise,  $[n - n_1]$  additional patients will be accrued for a total of  $[n]$ . The null hypothesis will be rejected if  $[r_2 + 1]$  or more responses are observed in  $[n]$  patients. This design yields a type I error rate of 0.1 and power of 80% when the true response rate is  $[p_1]$ .

**Table 15.2-1: Summary of Sample Size and Power for Expansion Cohorts**

Cohort	p0 Background ORR (%)	p1 Target ORR (%)	$\alpha$	Power (%)	n1 for Stage 1 (r1)	n2 (n - n1) for Stage 2	Total n (r2)
2a	2%	15%	0.1	80	11 (0)	15	26 (1)
2b	2%	15%	0.1	80	11 (0)	15	26 (1)
2c expansion	2%	15%	0.1	80	11 (0)	15	26 (1)
3a	2%	15%	0.1	80	11 (0)	15	26 (1)
3b	2%	15%	0.1	80	11 (0)	15	26 (1)
3c	2%	15%	0.1	80	11 (0)	15	26 (1)
3d	2%	15%	0.1	80	11 (0)	15	26 (1)
3e	2%	15%	0.1	80	11 (0)	15	26 (1)
3f	10%	25%	0.1	80	13 (1)	21	34 (5)
3g	20%	40%	0.1	80	12 (2)	13	25 (7)
3h	13%	30%	0.1	80	10 (1)	23	33 (6)

Cohort 2c is designed to generate additional evidence of clinical activity in a variety of tumor types. The sample size for the initial 30 patients was not based on a predefined statistical analysis. The sample size for each tumor type in any subsequent expansion of Cohort 2c will be guided by a Simon 2-stage design.

Part 1c is intended to enroll the minimum number of patients required to generate sufficient PK data for a descriptive comparison of Day 1 and steady state (Day 8, Day 15) exposures between patients with moderate renal impairment (CrCl 30-49 mL/min) and normal renal function (CrCl

> 50 mL/min). Accordingly, the sample size of 6 PK-evaluable patients for Cohort 1c is not based on a predefined statistical analysis.

### **15.3 Analysis Populations**

#### **15.3.1 Safety Population**

All patients who receive at least 1 dose of INCB001158 or pembrolizumab will be included in the analysis of safety, regardless of the duration of treatment.

AE and laboratory data from all patients in the safety population will be evaluated for safety. Patients from dose escalation will be combined with patients receiving the same dose and schedule from cohort expansion for safety evaluation. Patients with moderate renal impairment in Part 1c will be evaluated separately. Data will be tabulated to examine the frequency, organ systems affected, and relationship to study treatments. No formal interim analysis is planned; however, safety data will be examined on an ongoing basis to ensure safety of the study patients and compliance with the trial dose escalation and expansion rules.

#### **15.3.2 DLT-Evaluable Populations in Dose Escalation**

DLTs will be evaluated during dose escalation. Unless doses are missed in Cycle 1 due to drug-related AE(s), a patient must receive at least 75% of the planned INCB001158 doses (43 of 56 total doses) to be considered evaluable for DLT. If a patient received less than 43 doses of INCB001158 in the first 28 days of treatment for reasons other than a DLT, the patient will be considered non-evaluable for DLT and replaced. For patients in Part 1b and Part 3, patients must receive both doses of pembrolizumab in Cycle 1 in order to be evaluable for DLT.

Patients who discontinue the study prior to receiving the requisite study treatment administrations for reasons that include, but are not limited to, clinical/radiographic progression, voluntary withdrawal, or complications that the Principal Investigator considers secondary to the patient's malignancy will not be considered evaluable for DLT and will be replaced.

#### **15.3.3 Efficacy Evaluable Populations**

The Response Evaluable Population includes all patients who received at least 1 dose of study treatment (INCB001158 or pembrolizumab), completed a baseline scan, and met at least 1 of the following criteria:

- The patient had at least 1 post-baseline scan.

- The patient discontinued from study treatment for any reason except unrelated toxicity or death, or withdrawal of consent.

The PFS Evaluable Population includes all patients who received at least 1 dose of study treatment (INCB001158 or pembrolizumab).

Patients enrolled in the expansion cohorts who do not meet the requirements for the Response Evaluable Population will be considered non-evaluable for response and will be replaced.

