#### **Statistical Methods**

##### **Sample Size Method**

The primary objective is to determine a dose level of INCB001158, as monotherapy and in combination with pembrolizumab, for which the rate of DLTs is less than 33%. Up to approximately 108 patients are planned for single agent dose escalation (Part 1a) and up to 108 patients for combination dose escalation (Part 1b).

Part 1c is intended to enroll the minimum number of patients required to generate sufficient PK data for a descriptive comparison of Day 1 and steady state (Day 8, Day 15) exposures between patients with moderate renal impairment (CrCl 30-49 mL/min) and normal renal function (CrCl > 50 mL/min). Accordingly, the sample size of 6 PK-evaluable patients for Cohort 1c is not based on a predefined statistical analysis.

In Parts 2a, 2b, and 3, the sample size for each tumor type within a treatment group will be guided by the Simon 2-stage design. Part 2c is designed to investigate the potential for clinical activity in a variety of tumor types. The sample size for the initial 30 patients was not based on a predefined statistical analysis. The sample size for each tumor type in any subsequent expansion of Cohort 2c will be guided by a Simon 2-stage design.

Each Simon 2 stage design will have a stopping rule to allow early termination of a particular tumor type within a treatment group at the end of Stage 1 if there is insufficient response observed, while enrolling enough patients to predict possible target responses worthy of cohort expansion and potentially further evaluation in future studies.

The proposed designs for each tumor type will be used for any planned Simon 2-stage design. Each Simon 2-stage design is set up to have a 1-sided Type I error of 0.1 and power of 80%. The response rates for each tumor type will be estimated with 95% confidence intervals.

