***Part 3g: INCB001158 in combination with pembrolizumab in PD-1/PD-L1 naïve patients with SCCHN***

This cohort will enroll patients with SCCHN that have received no more than one prior therapy in the advanced/metastatic setting and have never received prior therapy with anti-PD-1/PD-L1, anti-CTLA4 or any other agent that specifically targets an immune checkpoint or co-stimulation pathway.

The primary endpoint will be ORR. Predose and postdose biopsies will be collected from patients enrolled to this cohort (unless it is not considered to be safe or otherwise is not feasible) until approximately 5 evaluable paired specimens are collected. Predose biopsies will be collected for all other patients, if feasible. [REDACTED]

[REDACTED]

[REDACTED]

*A Simon's two-stage design will test the null hypothesis that the ORR  $\leq 0.20$  versus the alternative that ORR  $\geq 0.40$ . A total of 12 response-evaluable patients will be enrolled in Stage 1. If at least 3 patients respond (PR or better) out of 12 response-evaluable patients, then an additional 13 evaluable patients will be enrolled in Stage 2 (total of 25 response-evaluable patients). If Stages 1 and 2 are completed, a minimum of 8 patients must demonstrate a response (PR or better) to reject the null hypothesis*

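### Patients who die before a post-baseline scan are replaced, not counted as non-responders; this biases the Simon decisions toward go and can push type I error above 0.10 in cohorts 3f, 3g and 3h

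*Protocol*

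**What the plan says.** Protocol 15.3.3 defines the Response Evaluable Population as patients with at least one dose and a baseline scan who meet one of two conditions. The first is a post-baseline scan. The second is: "The patient discontinued from study treatment for any reason except unrelated toxicity or death, or withdrawal of consent". Expansion-cohort patients who "do not meet the requirements for the Response Evaluable Population will be considered non-evaluable for response and will be replaced".

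The Part 3 decision rules are written in that population. For cohort 3g, Stage 2 opens as follows: "If at least 3 patients respond (PR or better) out of 12 response-evaluable patients". Cohorts 3f and 3h are worded the same way, with 3f restricted to MSS patients. SAP 5.3.4 refers back to 15.3.3 and uses that population for all efficacy except PFS.

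On error rates, the synopsis says "Each Simon 2-stage design is set up to have a 1-sided Type I error of 0.1 and power of 80"%, and Protocol 15.2 says "This design yields a type I error rate of 0.1 and power of 80"% at the target rate. SAP 7.2 says that p0 comes from a historical response rate but does not give its denominator.

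Protocol 15.4 also plans additional efficacy analyses in an expanded population that restores patients without post-treatment scans because of toxicity or death.

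**The concern.** Two patients with the same early course are handled differently. One stops treatment for progression before the first scan and counts as a non-responder. The other dies of the same progression before the scan and is removed, and another patient is enrolled in that place. Both are treatment failures.

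The wording leaves open whether unrelated qualifies only toxicity or also death. On the first reading every unscanned death is excluded. On the second, deaths attributed to treatment stay in, but a death from the cancer would normally be judged unrelated and is still excluded. The problem survives either way.

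An unscanned patient cannot be a documented responder, so removal and replacement can only raise the observed rate. At stake are the Stage 1 gate, the final rejection count and the reported ORR. Such deaths are foreseeable: Part 3 imaging is about every 9 weeks (Protocol 11.3) and the entry criterion on life expectancy is 3 months (Protocol 7.1).

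**Working it through.** **Inputs.** Protocol Table 15.2-1 gives p0, p1, n1 (r1) and n (r2):
- 3f: 10%, 25%, 13 (1), 34 (5)
- 3g: 20%, 40%, 12 (2), 25 (7)
- 3h: 13%, 30%, 10 (1), 33 (6)
- 2a, 2b, 2c expansion and 3a to 3e: 2%, 15%, 11 (0), 26 (1)

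The share d of patients removed and replaced is not in the documents, so it is an assumption, shown from 0 to 20%. It covers all replaced patients without a scan: deaths, unrelated toxicity and withdrawal of consent.

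**Formula.** P(reject | p) = sum over x from r1+1 to n1 of P[Bin(n1, p) = x] × P[Bin(n − n1, p) ≥ r2 + 1 − x].

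**Step 1: reproduce the plan.** For 3g at p = 0.20, the terms for x = 3 to 7 are 0.2362×0.0991, 0.1329×0.2527, 0.0532×0.4984, 0.0155×0.7664 and 0.0033×0.9450. Terms from x = 8 add 0.0006. The sum is 0.0234 + 0.0336 + 0.0265 + 0.0119 + 0.0031 + 0.0006 = 0.099. Type I error and power as designed are:
- 3f: 0.096 and 0.811
- 3g: 0.099 and 0.815
- 3h: 0.097 and 0.801
- 2%/15% cohorts: 0.067 and 0.804

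The stated 0.10 and 80% are met. The first three have almost no slack below 0.10.

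**Step 2: effect of replacement if p0 is an all-treated rate.** Of 100 treated patients, 100·p0 respond, and all of them lie among the 100(1 − d) who are counted. The null rate in the counted set is therefore p0/(1 − d). For 3g at d = 5% it is 0.20/0.95 = 0.2105, and the same sum gives 0.125.

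| d | 3f | 3g | 3h | 2%/15% cohorts |
|---|---|---|---|---|
| 0 | 0.096 | 0.099 | 0.097 | 0.067 |
| 2% | 0.103 | 0.109 | 0.105 | 0.069 |
| 5% | 0.115 | 0.125 | 0.119 | 0.073 |
| 10% | 0.139 | 0.158 | 0.146 | 0.080 |
| 15% | 0.167 | 0.199 | 0.179 | 0.088 |
| 20% | 0.203 | 0.252 | 0.220 | 0.097 |

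Type I error reaches 0.10 at d = 1.2% (3f), 0.2% (3g), 0.7% (3h) and about 21% (2%/15% cohorts). One replaced patient in a full cohort (1 in 35, 26 and 34) gives 0.106, 0.118 and 0.109 in 3f, 3g and 3h.

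**Step 3: if p0 is a rate among evaluable patients.** The null rate in the counted set is p0 itself, and the d = 0 row applies whatever d is.

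**Step 4: whether the expanded analysis helps.** Protocol 15.4 attaches no decision rule to it. In SAP Appendix A every ORR table, confirmed and unconfirmed, is on the efficacy-evaluable population. SAP 9.1 nevertheless records no change to protocol-defined analyses.

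**The case against.** The strongest reply is that Protocol 15.4 defines ORR as a proportion of efficacy-evaluable patients and the Simon rules use the same denominator. Read literally, the null hypothesis concerns that rate, and the exact type I error is 0.096, 0.099 and 0.097, as claimed. This stands as far as it goes. A reader might infer that the 0.10 level is broken as a matter of fact, and the documents do not show that. But the reply needs the historical p0 to rest on the same exclusions, and nothing in the documents says so.

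Second, a reader might infer that the counts are taken in survivors only. They are not. A patient who stops for progression or related toxicity before a scan stays in as a non-responder, even if death follows before week 9. Protocol 11.4 also requires imaging at end of treatment for anyone without a post-baseline image, and entry requires ECOG 0-1. The excluded share is therefore smaller than the share dying before the first scan and could be low, which is why the small values of d are tabulated.

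Third, it would be wrong to say that the excluded patients are never analysed. Protocol 15.4 plans to add them back, and PFS uses all treated patients. Neither feeds the go decision.

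Fourth, SAP 3.2 calls all analyses exploratory and SAP 7.1 says there is no primary efficacy endpoint. This limits the consequence. SAP section 3 still uses these designs to judge whether activity warrants further testing.

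**Conclusion.** The point holds in conditional form. As written, the evaluability rule removes and replaces unscanned deaths, at least those unrelated to treatment, and the Simon counts and main ORR inherit a bias in one direction, toward go. The direction does not depend on any assumption. The size does: type I error exceeds 0.10 in 3f, 3g and 3h only if p0 is an all-treated rate and the replaced share passes the thresholds above. The documents give neither the denominator of p0 nor the replaced share. Under that condition the excess is modest at 5% and clear at 10%. The eight 2%/15% designs have enough slack that the level is not at issue below about 20% replacement. Stronger statements, that the level is not held or that only survivors are counted, go beyond the documents.

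**What to change.** In Protocol 15.3.3 and SAP 5.3.4, for the Simon Stage 1 and final counts and the main ORR, count every treated patient with a baseline scan who dies from any cause before a post-baseline scan as a non-responder, and do not replace that patient. This also settles what unrelated qualifies. Keep the present response-evaluable set as a supportive analysis, with its own ORR table. State in Protocol 15.2 or SAP 7.2 whether p0 and p1 are all-treated or evaluable-basis rates.

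No sample size or cut-off changes. If p0 is an all-treated rate and deaths are the only replaced patients, type I error and power return to the d = 0 values. Replacement for unrelated toxicity or withdrawal of consent would continue, and its effect can be read from the same table with d set to that share.

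Costs: wording in two places, fewer replacement patients and a slightly lower ORR. If p0 and p1 are evaluable-basis rates, the counted target rate becomes p1(1 − d) and power drops. At d = 5% the rates are 0.25×0.95 = 0.2375, 0.40×0.95 = 0.38 and 0.30×0.95 = 0.285, giving power 0.771, 0.759 and 0.759 in 3f, 3g and 3h. At 10% it is 0.725, 0.694 and 0.710. The denominator of p0 and p1 should therefore be settled first.
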